## **Vaccines to Prevent Pneumococcal Disease**

### **Pneumococcal Polysaccharide Vaccines**

The polysaccharide capsule has been identified as an important virulence factor for this pathogen. While more than 95 pneumococcal serotypes, differentiated by their capsular polysaccharide composition, have been identified, serious disease is generally caused by a smaller subset of serotypes. Anticapsular antibodies directed against the specific serotype bind to the capsule and promote complement-mediated opsonophagocytic killing and clearance of the organism. Pneumococcal disease can be prevented with polysaccharide-based vaccines that induce antibody responses with functional OPA activity and target the capsular serotypes responsible for disease.

Vaccines containing free polysaccharides have been licensed since the 1970s. One such vaccine, the 23-valent pneumococcal polysaccharide vaccine (PPSV23), has been licensed in the United States since 1983. PPSV23 contains capsular polysaccharides for 23 serotypes (1, 2, 3, 4, 5, 6B, 7F, 8, 9N, 9V, 10A, 11A, 12F, 14, 15B, 17F, 18C, 19F, 19A, 20, 22F, 23F, and 33F). Pneumococcal vaccines containing free polysaccharides such as PPSV23 elicit a T-cell-independent immune response. Unconjugated polysaccharide vaccines do not induce robust responses in certain populations (eg, immunocompromised persons, and children <2 years of age), nor do they generate immunologic memory, so that their protective effect wanes over 2 to 5 years. Moreover, their ability to prevent nonbacteremic pneumonia, CAP, and AOM is limited or lacking. In addition, polysaccharide vaccines do not reduce VT nasopharyngeal carriage, which is important for herd immunity. PPSV23 is not recommended for children <2 years of age and only recommended in children >2 years of age who are at high risk for IPD to provide some degree of protection from disease caused by serotypes not covered by existing pneumococcal conjugate vaccines.

### **Pneumococcal Polysaccharide Conjugate Vaccines**

Pneumococcal conjugate vaccines contain polysaccharides that are covalently linked (conjugated) to an immunogenic protein. This modification results in T-cell-dependent immune responses, which have been shown to be protective in young children, older adults, and populations with high-risk conditions. 7vPnC was the first pneumococcal conjugate vaccine to be licensed (2000) and was indicated for prevention of pneumococcal disease in infants and young children on the basis of efficacy studies. 7vPnC contained capsular

polysaccharide conjugates for 7 pneumococcal serotypes (4, 6B, 9V, 14, 18C, 19F, and 23F), each covalently linked to CRM197, a nontoxic variant of diphtheria toxin. These 7 serotypes were responsible for approximately 80% to 90% of IPD in children <5 years of age in the United States and approximately 60% to 80% of IPD in the same age group in Europe at that time (1998-2000). These serotypes also accounted for a high proportion of antibiotic-resistant strains. 7vPnC demonstrated efficacy against VT IPD, pneumonia, and AOM in large randomized, controlled efficacy studies in infants. The 7vPnC components contained in a related pneumococcal conjugate vaccine also were demonstrated to be efficacious against clinically/radiographically defined pneumonia. Following introduction of 7vPnC, reduction of nasopharyngeal carriage and transmission has resulted in indirect herd effects, with a 92% reduction of 7vPnC VT IPD in older adults ≥65 years of age.

13vPnC was developed to expand serotype coverage and was licensed in the United States in 2010. 13vPnC includes the same *S pneumoniae* serotypes as 7vPnC and an additional 6 polysaccharide conjugates for serotypes 1, 3, 5, 6A, 7F, and 19A. The vaccine was licensed for use in infants and young children based on comparisons of serotype-specific serum IgG antibody concentrations to 7vPnC, with supportive data to demonstrate the functional activity of the immune responses. 13vPnC has also been licensed in adults based on demonstration of efficacy against CAP due to serotypes contained in 13vPnC in adults 65 years of age and older. 13vPnC has replaced 7vPnC and is licensed in the United States and many other countries including Japan, with national recommendations for use in children and older adults. It has also been prequalified by the WHO for use in national infant immunization programs in lower- and middle-income countries. Surveillance data from several countries following introduction of 13vPnC into the routine infant immunization program have demonstrated vaccine effectiveness against 13vPnC VT IPD in the vaccinated population.

## Development of 20vPnC

The 20vPnC candidate is modeled after 7vPnC and 13vPnC, and contains polysaccharides of capsular serotypes of *S pneumoniae*, each covalently linked to CRM197. The amount of polysaccharide (2.2 µg/dose) selected for each new serotype (8, 10A, 11A, 12F, 15B, 22F, and 33F) contained in the 20vPnC candidate mirrors the approach taken for the addition of the 6 new serotypes when developing 13vPnC. The 20vPnC candidate contains the same components as 13vPnC, including the 13 polysaccharide conjugates, excipients (polysorbate 80, succinate buffer, sodium chloride), and aluminum phosphate, in addition to the 7 new polysaccharide conjugates. Additional epidemiology data of the 7 serotypes and the preclinical program are described in the 20vPnC IB. The vaccine is being developed for use in pediatric and adult populations.

### 2.1. Study Rationale

CCI

In Japan, 7vPnC and 13vPnC have been administered to infants by SC injection on a 4-dose vaccination schedule (3 doses for infant series and 1 dose

for toddler dose). CCI [REDACTED]

CCI [REDACTED]

The targeted age of the population for this study, infants  $\geq 2$  to  $\leq 6$  months of age, has been selected as the routinely recommended vaccination schedule for pneumococcal conjugate vaccines and other vaccines in infants starts at approximately 2 months of age. The participants will be administered either 20vPnC (SC or IM injection) or 13vPnC SC by the same injection route for all 4 doses starting from 2 months of age.

## 2.2. Background

20vPnC is being developed to further expand protection against the global burden of vaccine-preventable pneumococcal disease in children and adults over that of 13vPnC. 20vPnC contains the serotypes present in 13vPnC, and 7 new serotypes (8, 10A, 11A, 12F, 15B, 22F, and 33F) individually conjugated to CRM197. As noted above, 20vPnC uses the same platform and contains the same excipients as 13vPnC. These 7 additional serotypes were selected based on their relative prevalence as a cause of IPD, their generalized geographic distribution, and other factors that would support inclusion, such as the presence of antibiotic resistance (11A, 15B), association with outbreaks (8, 12F), and greater disease severity (eg, meningitis, mortality) (10A, 11A, 22F). These 7 serotypes have a long-standing association with serious pneumococcal disease and are responsible for a substantial burden of remaining pneumococcal disease. The incidence of IPD due to these 7 serotypes in children  $< 5$  years of age has remained relatively stable or slightly increased over the past several years, and these serotypes cause a significant amount of IPD in children. These 7 serotypes contribute to the burden of IPD in the United States and elsewhere. It is estimated that between 2015 and 2016, these 7 serotypes accounted for 34% to 39% of IPD in children in the United States. In the EU, according to the ECDC annual IPD epidemiological report, in 2017, approximately 75% of cases of IPD in children  $< 5$  years of age were caused by a serotype not in 13vPnC, increased from 63% in 2013. Five of the 10 most common serotypes included serotypes 8, 10A, 11A, 12F, and 22F, with serotypes 8, 10A, 12F, and 24F being among the most common in children in this age group.

A meta-analysis of serotypes causing IPD in children  $< 5$  years of age in regions of the world (including Japan) that have introduced higher-valent pneumococcal conjugate vaccines (such as 13vPnC) showed that, overall, these 7 new serotypes accounted for approximately 70% of disease not due to the 13vPnC vaccine types.

### 2.2.1. Clinical Overview

Safety and immunogenicity data from a 20vPnC Phase 1 study (B7471001) conducted in healthy adults 18 through 49 years of age demonstrated that the vaccine induced immune responses to the 20 vaccine serotypes and had a safety profile consistent with other

pneumococcal conjugate vaccines. These data supported clinical development in other populations, including pediatric populations.

A Phase 1 study (B7471005) of 20vPnC in healthy Japanese adults 18 through 49 years of age was conducted in the United States. The administration of 20vPnC by IM injection was well tolerated and induced immune responses to the 20 vaccine serotypes. These data support continued development of 20vPnC in Japan.

A Phase 2 study (B7471003) of 20vPnC in healthy infants  $\geq 42$  to  $\leq 98$  days of age has been conducted. The study randomized 460 US participants to receive either blinded 20vPnC or 13vPnC by IM injection. Safety and immunogenicity data are available from this study. 20vPnC was well tolerated in the infants and the safety profile was similar to that of the 13vPnC group in the study and consistent with other pneumococcal conjugate vaccines. Immune responses (either IgG GMCs or percentages of participants meeting a predefined IgG concentration) after 3 doses of 20vPnC were similar to those in the 13vPnC group. These data support continued development of 20vPnC in a pediatric population.

### **2.3. Benefit/Risk Assessment**

More detailed information about the known and expected benefits and risks and reasonably expected AEs of 20vPnC may be found in the IB, which is the SRSD for this study. The SRSD for the 13vPnC agent is the Japan package insert.

### 2.3.1. Risk Assessment

Potential Risk of Clinical Significance	Summary of Data/Rationale for Risk	Mitigation Strategy
20vPnC and 13vPnC		

13vPnC is a licensed vaccine and the most common AEs noted in children <5 years of age after vaccination are primarily related to local reactions (injection site pain or tenderness, redness, and swelling) and systemic events (fever, irritability, decreased appetite, and increased sleep).
 
As with any vaccine, an allergic reaction can occur. The allergic reaction can vary from skin rash to swelling of the face or lips, wheezing, and/or shortness of breath. A severe allergic reaction (anaphylactic shock, collapse, or shock-like state [hypotonic-hyporesponsive episode]) may also occur. There may also be additional risks related to the vaccines administered in the study that are not known at this time.
	
The 20vPnC investigational product contains the same components and excipients as 13vPnC, and also contains the polysaccharide conjugates for the 7 additional pneumococcal serotypes. Thus, the AE profile of 20vPnC is expected to be similar to 13vPnC, but AEs may be different with the investigational 20vPnC.
 
In a randomized, active-controlled, double-blind study with a 2-arm parallel design (B7471003), 20vPnC was administered intramuscularly to 460 infants <math>\geq 42</math> to <math>\leq 98</math> days of age naive to pneumococcal vaccine. The vaccine was well tolerated and the AE profile was consistent with events commonly seen in this age group. The most common AEs after 20vPnC administration were local reactions (pain, redness, and swelling at the injection site) and systemic events (irritability, drowsiness/increased sleep, and decreased appetite).
	
Safety assessments (ie, local reactions, systemic events, AEs [including observation for 30 minutes after vaccination], SAEs, and NDCMCs) described in the protocol and ongoing review of safety data by the investigator and sponsor study team will serve to monitor and mitigate these risks.
 
CCI [REDACTED]


This study is the first study that 20vPnC will be administered subcutaneously and the study participants are infants.
	
The 20vPnC investigational product contains the same components and excipients as 13vPnC, and also contains the polysaccharide conjugates for the 7 additional pneumococcal serotypes. Thus, the AE profile of 20vPnC is expected to be similar to 13vPnC, but AEs may be different with the investigational 20vPnC.
 
In a clinical study of 13vPnC administered by SC injection in Japan, local reactions at the 13vPnC injection site (SC injection), particularly redness
	
Daily enrollment will be limited initially with enhanced monitoring of the safety and tolerability of the study vaccine after Dose 1. If there are no unexpected safety concerns after Dose 1 in the first 45 participants, the daily enrollment limit will be removed. Ongoing regular monitoring and review of safety and tolerability of the blinded study data by the study team.

Potential Risk of Clinical Significance	Summary of Data/Rationale for Risk	Mitigation Strategy
20vPnC and 13vPnC		
	
and swelling, occurred at somewhat higher rates compared with studies that administered 13vPnC by IM injection. However local reactions in the study were generally mild or moderate, consistent with other published studies of 13vPnC.
 
In another clinical study of 13vPnC administered by SC injection in Japan, local reactions, particularly redness and swelling, occurred at higher rates at the 13vPnC injection site were comparable with those of 7vPnC administered by SC injection.
	
Study Procedures		

Risks that may be associated with study procedures include risks from blood sample collection, including pain, swelling, bruising, and infection where blood is taken.
	
Risks and possible discomforts from the study procedures such as pain, swelling, bruising, infection around the vein where the child's blood is collected may also occur, although this is very uncommon.
	
The volume and frequency of blood sample collection required during the study has been minimized as far as possible.

### 2.3.2. Benefit Assessment

13vPnC is approved in Japan (and in many other countries worldwide) for the prevention of IPD due to the serotypes in the vaccine, and should provide a clinical benefit to those receiving the vaccine. In the B7471003 study, 20vPnC induced immune responses to the pneumococcal serotypes in the vaccine. This suggests that protection against pneumococcal disease will be similar to 13vPnC. If 20vPnC is successful in Phase 3 studies, and approved, it is anticipated to provide a public health benefit by reducing the burden of IPD due to pneumococcal serotypes contained in the vaccine.

### 2.3.3. Overall Benefit/Risk Conclusion

Pfizer considers that the available information from Study B7471003 with 20vPnC, the available safety profile of similar pneumococcal conjugate vaccines (ie, Prevenar and Prevenar 13), and the limited risks from study procedures support a favorable benefit-risk profile for 20vPnC and this study.

## 3. OBJECTIVES, ESTIMANDS, AND ENDPOINTS

Primary Safety Objective	Estimands	Primary Safety Endpoints

 
To describe the safety profile of 20vPnC by both SC injection and IM injection
 
	
In participants receiving at least 1 dose of investigational product and having safety data reported after any vaccination:
 
 
The percentage of participants reporting prompted local reactions at injection site of investigational product within 7 days after each vaccination in each group
 
The percentage of participants reporting prompted systemic events within 7 days after each vaccination in each group
 
The percentage of participants reporting AEs from Dose 1 to 1 month after Dose 3 in each group
 
The percentage of participants reporting AEs from Dose 4 to 1 month after Dose 4 in each group
 
The percentage of participants reporting SAEs up to 1 month after Dose 4 in each group
 
The percentage of participants reporting NDCMCs up to 1 month after Dose 4 in each group
 
	
 
Prompted local reactions (redness, swelling, and pain at the injection site)
 
Prompted systemic events (fever, decreased appetite, drowsiness/increased sleep, and irritability)
 
AEs
 
SAEs
 
NDCMCs
 

Primary Immunogenicity Objectives	Estimands	Primary Immunogenicity Endpoints
For 20vPnC SC group:		

 
To demonstrate the percentage of participants with predefined serotype-specific IgG concentrations for the 13 serotypes in the 20vPnC SC group are noninferior to the percentage of the corresponding serotypes in the 13vPnC SC group at 1 month after Dose 3
 
To demonstrate the percentage of participants with predefined serotype-specific IgG concentrations for the 7 additional serotypes in the 20vPnC SC group are noninferior to the lowest percentage among the 13 serotypes in the 13vPnC SC group at 1 month after Dose 3
 
	
In participants in compliance with the key protocol criteria (evaluable participants) at 1 month after Dose 3:
 
 
For each of the 13 matched serotypes: difference in the percentage of participants with predefined serotype-specific IgG concentrations between the 20vPnC SC group and the 13vPnC SC group
 
 
In evaluable participants at 1 month after Dose 3:
 
 
For each of the 7 additional serotypes in 20vPnC: difference in the percentage of participants with predefined serotype-specific IgG concentrations, between the 20vPnC SC group and the lowest percentage of participants with predefined serotype-specific IgG concentrations among the 13 serotypes from the 13vPnC SC group
 
	
 
Pneumococcal serotype-specific IgG concentration
 
Pneumococcal serotype-specific IgG concentration
 

For 20vPnC IM group:		

 
To describe the immune responses to 20 serotypes induced by 20vPnC given by IM injection at 1 month after Dose 3
 
	
In evaluable participants at 1 month after Dose 3:
 
 
For each of the serotypes in 20vPnC: difference in the percentage of participants with predefined serotype-specific IgG concentrations between the 20vPnC IM group and the 20vPnC SC group
 
	
 
Pneumococcal serotype-specific IgG concentration
 

Secondary Immunogenicity Objectives	Estimands	Secondary Immunogenicity Endpoints

 
To demonstrate the serotype-specific IgG GMCs for the 13 serotypes in the 20vPnC SC group are noninferior to the GMCs for the corresponding serotypes in the 13vPnC SC group at 1 month after Dose 3
 
	
In evaluable participants at 1 month after Dose 3:
 
 
For each of the 13 matched serotypes: GMR of serotype-specific IgG concentrations from the 20vPnC SC group to the 13vPnC SC group
 
	
 
Pneumococcal serotype-specific IgG concentrations
 

 
To demonstrate the serotype-specific IgG GMCs for the 7 additional serotypes in the 20vPnC SC group are noninferior to the lowest IgG GMC among the 13 serotypes induced by the 13vPnC SC group at 1 month after Dose 3
 
	
In evaluable participants at 1 month after Dose 3:
 
 
For each of the 7 additional serotypes in 20vPnC: GMR of serotype-specific IgG concentration from the 20vPnC SC group to the serotype with the lowest IgG GMC among the 13 serotypes from the 13vPnC SC group
 
	
 
Pneumococcal serotype-specific IgG concentrations
 


 
To further describe the immunogenicity of 20vPnC by both SC and IM injection
 
	
In evaluable participants at 1 month after Dose 3:
 
 
For each of the serotypes in 20vPnC: GMR of serotype-specific IgG concentrations from the 20vPnC IM group to the 20vPnC SC group
 
 
In evaluable participants at 1 month after Dose 4:
 
 
For each of the serotypes in 20vPnC: Serotype-specific IgG GMCs at 1 month after Dose 4 in each group
 
 
In evaluable participants at 1 month after Dose 3 and 1 month after Dose 4:
 
 
Serotype-specific OPA GMTs at 1 month after Dose 3, prior to Dose 4, and 1 month after Dose 4 in each group
 
 
In evaluable participants at 1 month after Dose 4:
 
 
For each of the serotypes in 20vPnC: percentage of participants with the predefined serotype-specific IgG concentration in each group
 
	
 
Pneumococcal serotype-specific IgG concentrations
 
Pneumococcal serotype-specific IgG concentrations
 
Pneumococcal serotype-specific OPA titers
 
Pneumococcal serotype-specific IgG concentrations
 

	In evaluable participants: 

• GMFRs in serotype-specific IgG concentrations from 1 month after Dose 3 to before Dose 4, from before Dose 4 to 1 month after Dose 4, and from 1 month after Dose 3 to 1 month after Dose 4 in each group

	• Pneumococcal serotype-specific IgG concentrations
CCI [REDACTED]	[REDACTED]	[REDACTED]
[REDACTED]	[REDACTED]	[REDACTED]

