## Statistical Methods

The primary safety objective will be evaluated by descriptive summary statistics for local reactions, systemic events, and AEs, including SAEs and NDCMCs, for each vaccine group. A 3-tier approach will be used to summarize AEs.

The primary pneumococcal immunogenicity objectives for the 20vPnC SC group will be evaluated by formal hypothesis test for noninferiority of 20vPnC to 13vPnC based on serotype-specific IgG results. At 1 month after Dose 3, noninferiority for a serotype will be declared if the lower bound of the 2-sided 95% CI for the between-group difference in percentage of participants with a predefined serotype-specific IgG concentration level (20vPnC SC – 13vPnC SC) is greater than –10% (10% noninferiority margin). The primary pneumococcal immunogenicity objectives for the 20vPnC SC group of the study for pneumococcal immunogenicity assessment at 1 month after Dose 3 will be achieved, in principle, if noninferiority of the pneumococcal immune response to 20vPnC SC compared to 13vPnC SC is met for all 20 serotypes; each of the 13 matched serotypes in the 20vPnC SC group relative to each serotype in the 13vPnC SC group, and each of the 7 additional serotypes in 20vPnC group relative to the lowest value in the 13vPnC SC group.

The primary pneumococcal immunogenicity objective for 20vPnC IM group will be evaluated by descriptive assessments for difference in the percentage of participants with a predefined serotype-specific IgG concentration level (20vPnC IM – 20vPnC SC) at 1 month after Dose 3.

CCI [REDACTED]

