#### 9.1.2.1. Noninferiority Comparing Percentage of Participants with Predefined Pneumococcal Serotype-Specific IgG Concentrations 1 Month after Dose 3 (Primary Endpoint)

Hypothesis testing will be used to assess noninferiority of 20vPnC SC to 13vPnC SC by the percentage of participants with predefined pneumococcal serotype-specific IgG concentrations 1 month after Dose 3. The null hypothesis ( $H_{0A}$ ) for each serotype is

$$H_{0A}: \pi_{20vPnC\ SC} - \pi_{13vPnC\ SC} \leq -10\%,$$

with a 10% margin for noninferiority, where

- $\pi_{20vPnC\ SC}$  is the percentage of participants achieving an IgG antibody concentration of a predetermined level in the 20vPnC SC group from the serotype 1 month after Dose 3;
- If the serotype is from the 13 matched serotypes (1, 3, 4, 5, 6A, 6B, 7F, 9V, 14, 18C, 19A, 19F, 23F),  $\pi_{13vPnC\ SC}$  is the percentage of participants achieving a predefined IgG concentration level for the serotype from the 13vPnC SC group 1 month after Dose 3;
- If the serotype is from the 7 additional serotypes (8, 10A, 11A, 12F, 15B, 22F, 33F) in 20vPnC,  $\pi_{13vPnC\ SC}$  is the percentage of participants achieving a predefined IgG concentration level from the serotype with the lowest percentage 1 month after Dose 3 among the 13 serotypes from the 13vPnC SC group, provided that the lowest percentage is not from serotype 3. If the lowest percentage in the 13vPnC SC group is from serotype 3, the next lowest percentage in the 13vPnC SC group will be used in the comparison. Historical data suggest that serotype 3 behaves somewhat differently from the other serotypes in 13vPnC; therefore, IgG results from serotype 3 will not be used in the comparison to assess the noninferiority of the 7 additional serotypes.

- The predefined levels for serotype-specific IgG concentrations are 0.35 µg/mL for all serotypes in 20vPnC except that the predefined levels are 0.23 µg/mL, 0.10 µg/mL, and 0.12 µg/mL for serotypes 5, 6B, and 19A, respectively.

The null hypothesis  $H_{0A}$  will be rejected and noninferiority of 20vPnC SC to 13vPnC SC for the percentage of participants with predefined IgG concentration level will be declared for a serotype if the lower bound of the 2-sided 95% CI for the difference (20vPnC SC group – 13vPnC SC group) in percentages, computed using the Miettinen and Nurminen method, is greater than –10% (10% noninferiority margin).

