### 9.4.1. Immunogenicity Analyses

The statistical analysis of immunogenicity results will be primarily based on the evaluable immunogenicity populations (primary immunogenicity population) as defined in [Section 9.3](#).

CCI [REDACTED]

Participants will be summarized according to the vaccine group to which they are randomized. Missing serology data will not be imputed.

Endpoint	Statistical Analysis Methods
Primary immunogenicity	

The difference of the percentage of participants with predefined pneumococcal serotype-specific IgG concentrations 1 month after Dose 3

 
For each of the 20 serotypes for 20vPnC SC and 13vPnC SC groups, between-group difference (20vPnC SC - 13vPnC SC) and the 2-sided 95% CI for the percentage of participants with predefined serotype-specific IgG concentrations 1 month after Dose 3 will be provided. If a serotype is from the 13 matched serotypes, the percentage of participants with the predefined IgG level for the serotype in the 20vPnC SC group will be compared with the percentage for that serotype in the 13vPnC SC group. If a serotype is from the 7 additional serotypes, the percentage of participants with the predefined IgG level in the 20vPnC SC group will be compared with the lowest percentage among the 13 serotypes from the 13vPnC SC group, provided that the lowest percentage is not from serotype 3. If the lowest percentage in the 13vPnC SC group is from serotype 3, the next lowest percentage in the 13vPnC group will be used in the comparison.
 
The lower limit of the CI will be used in the hypothesis test for NI of 20vPnC to 13vPnC as detailed in Section 9.1.2.1.

Endpoint	Statistical Analysis Methods

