### 5.1. Hypotheses and Decision Rules

#### 5.1.1. Immunogenicity Hypotheses

##### 5.1.1.1. Percentage of Participants With Predefined Pneumococcal Serotype-Specific IgG Concentration 1 Month After Dose 3 (Primary Immunogenicity Objectives)

Hypothesis testing will be used to assess the NI of 20vPnC SC to 13vPnC SC for percentages of participants with predefined pneumococcal serotype-specific IgG concentrations 1 month after Dose 3 (see [Section 3.1.2](#) for predefined concentrations). The null hypothesis ( $H_{0A}$ ) for a serotype is

$$H_{0A}: \pi_{20vPnC\ SC} - \pi_{13vPnC\ SC} \leq -10\%,$$

with a 10% margin for NI, where

- $\pi_{20vPnC\ SC}$  is the percentage of participants achieving the IgG concentration of predefined level in the 20vPnC SC group for the serotype 1 month after Dose 3.
- If the serotype is from the 13 matched serotypes (1, 3, 4, 5, 6A, 6B, 7F, 9V, 14, 18C, 19A, 19F, 23F) in 13vPnC,  $\pi_{13vPnC\ SC}$  is the percentage of participants achieving the predefined IgG concentration level for the serotype from the 13vPnC SC group 1 month after Dose 3.
- If the serotype is from the 7 additional serotypes (8, 10A, 11A, 12F, 15B, 22F, 33F) in 20vPnC,  $\pi_{13vPnC\ SC}$  is the percentage of participants achieving a predefined IgG concentration level from the serotype with the lowest percentage 1 month after Dose 3 among the 13 serotypes from the 13vPnC SC group, provided that the lowest percentage is not from serotype 3. If the lowest percentage in the 13vPnC SC group is from serotype 3, the next lowest percentage in the 13vPnC SC group will be used in the comparison. Historical data suggest that serotype 3 behaves somewhat differently from the other serotypes in 13vPnC; therefore, IgG results from serotype 3 will not be used in the comparison to assess the NI of the 7 additional serotypes.

The null hypothesis ( $H_{0A}$ ) will be rejected and NI of the 20vPnC SC group to the 13vPnC SC group for the percentage of participants with the predefined IgG concentration level will be declared for a serotype if the lower bound of the 2-sided 95% CI for the difference (20vPnC SC group – 13vPnC SC group) in percentages, based on the Miettinen and Nurminen method, is greater than –10% (10% NI margin).

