###### 6.1.2.1.1. Main Analysis

- (For 20vPnC SC) Estimands:
  - For each of the 13 matched serotypes in 20vPnC, the difference in percentages of participants with predefined serotype-specific IgG concentrations between the 20vPnC SC group and the 13vPnC SC group ([Section 2.1](#)).

- For each of the 7 additional serotypes in 20vPnC, the difference in the percentages of participants with predefined serotype-specific IgG concentrations between the 20vPnC SC group and the lowest percentage of participants with predefined serotype-specific IgG concentrations among the 13 serotypes from the 13vPnC SC group, excluding serotype 3.
- (For 20vPnC IM) Estimand: For each of the 20 serotypes in 20vPnC, the difference in percentages of participants with predefined serotype-specific IgG concentrations between the 20vPnC IM group and the 20vPnC SC group ([Section 2.1](#)).
- Analysis set: Dose 3 evaluable immunogenicity population ([Section 4](#)).
- Analysis time point: 1 Month after Dose 3.
- Analysis methodology: The between-group difference (20vPnC SC – 13vPnC SC and 20vPnC IM – 20vPnC SC) and the corresponding 2-sided 95% CI will be calculated using the Miettinen and Nurminen method ([Section 5.2.1](#)) for each serotype. NI of 20vPnC SC relative to 13vPnC SC will be assessed by comparing the lower bound of the 95% CI for the between-group difference ([Section 5.1.1.1](#)).
- Intercurrent events and missing data: Serology data deemed unevaluable because of noncompliance with the key protocol criteria will be excluded. Missing data will not be imputed.
- Reporting results: For each of the 20 vaccine serotypes, the numerator (n), the denominator (N) used in the percentage calculation, the percentage (%), and the corresponding 2-sided 95% CI for participants with predefined IgG concentrations from each vaccine group, as well as the percentage difference and the associated 95% CI, will be presented.

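### Does leaving serotype 3 in the stated objective, but out of the test, make the comparator for the 7 new serotypes ambiguous?

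*Protocol*

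**What the plan says.** Two sets of places describe the comparator for the 7 additional serotypes.

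**Without an exclusion.** The Protocol Section 3 objective asks that these serotypes be "noninferior to the lowest percentage among the 13 serotypes in the 13vPnC SC group at 1 month after Dose 3", and its estimand uses "the lowest percentage of participants with predefined serotype-specific IgG concentrations among the 13 serotypes from the 13vPnC SC group". The synopsis objectives table and SAP Table 2 follow the same form. The synopsis success rule, under Statistical Methods, tests "each of the 7 additional serotypes in 20vPnC group relative to the lowest value in the 13vPnC SC group".

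**With serotype 3 removed.** Protocol 9.1.2.1 states that "IgG results from serotype 3 will not be used in the comparison to assess the noninferiority of the 7 additional serotypes", because serotype 3 has behaved differently in historical data, and moves to the next lowest percentage if serotype 3 is the minimum. Protocol 9.4.1 uses the minimum "provided that the lowest percentage is not from serotype 3". SAP 5.1.1.1 repeats that "IgG results from serotype 3 will not be used in the comparison to assess the NI of the 7 additional serotypes". The estimand in SAP 6.1.2.1.1 takes the minimum "among the 13 serotypes from the 13vPnC SC group, excluding serotype 3".

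The secondary GMC comparison splits in the same way. The objectives and estimands in Protocol Section 3 and SAP Table 2 are silent on serotype 3, while Protocol 9.1.2.2 and SAP 5.1.1.2 and 6.2.1.1.1 exclude it.

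**The concern.** A primary comparator should have one definition. Here the objectives table names the minimum over 13 serotypes and the test uses the minimum over 12. The two coincide unless serotype 3 is the lowest in the 13vPnC SC group, and that is the case the exclusion was written for. The synopsis counts the primary objective as met, in principle, only if all 20 serotypes pass, so a single new serotype lying between the two comparators would settle the outcome. A result could then satisfy the objective as worded and fail the planned test, leaving room to argue after unblinding about which one counts.

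**Working it through.** **Inputs from the documents.** 200 evaluable infants per group (Protocol 4.1.2); Miettinen and Nurminen 2-sided 95% CI "with a 10% margin for noninferiority" (Protocol 9.1.2.1). The responder percentages behind Table 6 are redacted, so its 92% power cannot be reproduced and every percentage below is an assumption.

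**Step 1: can the two wordings disagree?** The score statistic at the margin is

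z = (p_new − p_comp + 0.10) / sqrt{ [a(1−a)/200 + b(1−b)/200] × 400/399 },

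where b is the restricted maximum likelihood estimate for the comparator and a = b − 0.10. Noninferiority needs z > 1.96. Take a new serotype observed at 170/200 (85%).

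- Against serotype 3 at 160/200 (80%): b = 0.860, a = 0.760, z = 0.15/0.0390 = 3.85. The 95% lower bound is -2.5%. Met.
- Against the next lowest at 180/200 (90%): b = 0.917, a = 0.817, z = 0.05/0.0336 = 1.49. The lower bound is -11.7%. Not met.

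So they can. With those comparators the verdict differs for observed new-serotype percentages from 78.5% to 86.0%. If serotype 3 is at 80% and the next lowest at 85%, the range is 78.5% to 82.0%.

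**Step 2: how large is the contrast?** Probability that one new serotype passes, n = 200 per group, comparator serotype fixed in advance:

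| True % of new serotype | Against serotype 3 | Against next lowest at 88% |
|---|---|---|
| 75 | 99% (serotype 3 at 65%) | 0.3% |
| 80 | 95% (serotype 3 at 75%) | 8% |
| 80 | 26% (serotype 3 at 85%) | 8% |
| 88 | 100% (serotype 3 at 75%) | 86% |
| 90 | 100% (serotype 3 at 75%) | 96% |
| 92 | 100% (serotype 3 at 75%) | 99.6% |

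The wide gaps appear only when the new serotype sits 8 to 13 points below the next lowest one. At or above it, the gap is at most 14 points. Joint power cannot exceed the power for any single serotype. If Table 6 was simulated with the planned comparator, its 92% for all 20 serotypes means each serotype had at least 92% under the planning assumptions, which excludes the first three rows.

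**Step 3: which way does the difference run?** The minimum over 12 serotypes is never below the minimum over 13. With equal denominators, any new serotype that passes the planned test also passes the all-13 comparison. The exclusion can turn a pass into a fail, and never the reverse.

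**Step 4: which wording would an analyst apply?** Four places specify the primary test or analysis: Protocol 9.1.2.1 and 9.4.1, SAP 5.1.1.1 and 6.1.2.1.1. All four exclude serotype 3. The three that specify the GMC comparison in full (Protocol 9.1.2.2, SAP 5.1.1.2 and 6.2.1.1.1) do the same. No analysis section runs the all-13 comparison. SAP 6.1.2.1.1 sets out estimand, analysis set, method and reporting together with the exclusion included, so the estimand reported is the one tested.

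**The case for a change.** The best argument for a change is that the abbreviated text is not mere summary. Protocol 9.1.1 sends the reader to the Section 3 table for the estimands, and SAP 2.1 sends the reader to Table 2. Neither table mentions serotype 3 or points forward to the exclusion, so SAP Table 2 and SAP 6.1.2.1.1 give different estimands for one objective. The only unredacted statement that all 20 serotypes must pass is in the synopsis, which also omits the exclusion. The sponsor plainly expected that serotype 3 might be lowest, and the repair is a few words.

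The description of the mismatch stands, and so do the simulated contrasts under their assumptions. What does not stand is the inference that the primary result is open to two readings. To apply the all-13 comparator, an analyst would have to prefer an objectives table or a synopsis sentence over every section that defines the hypothesis, the fallback and the reporting, two of which (Protocol 9.1.2.1 and SAP 5.1.1.1) explain why serotype 3 is left out. In SAP 6.1.2.1.1 the matched-serotype estimand cites Section 2.1, whereas the one for the 7 additional serotypes drops that citation and adds the exclusion. That is consistent with a deliberate refinement of Table 2. A sponsor wanting to argue for the lenient reading after unblinding would be arguing against its own prespecified test.

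**Conclusion.** No change to the plan is called for. The synopsis, Protocol Section 3 and SAP Table 2 shorten the comparator and leave out an exclusion that the hypothesis and analysis sections state consistently. Followed as written, the plan tests and reports one comparator, the lowest of the 12 serotypes other than serotype 3. That comparator is at least as demanding as the shortened wording, so the mismatch neither raises the type I error nor supports a false claim of noninferiority. The wordings diverge only if serotype 3 is lowest in the 13vPnC SC group and a new serotype falls between the two thresholds, for example 78.5% to 86.0% observed when serotype 3 is at 80% and the next lowest at 90%. Those percentages are assumed, because the documents show none. Aligning the wording would leave the test, margin, sample size and conclusions as they are.
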